10.2 STATISTICAL HYPOTHESES

- Primary Efficacy Endpoints: SNOT-22
 - H₀: There is no means difference between baseline SNOT-22 scores and 4 week SNOT-22 scores
- Secondary Efficacy Endpoints: VAS and LKS
 - o H₀: There is no means difference between baseline VAS scores and 4 week VAS scores
 - o H₀: There is no means difference between baseline LKS scores and 4 week LKS scores

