The Phase II study will be an open label safety and efficacy expansion cohort using the MTD determined in the Phase IB arm. A total of 20 patients will be administered the MTD of topical Verapamil HCl in a 240mL buffered normal nasal rinse for 4 weeks BID. This sample size was calculated based on a power analysis derived from the results of our oral Verapamil trial. The first dose will be administered in in a 10th or 11th floor MEE clinic withhemodynamic monitoring. A medically trained member of the study staff with monitor the patient for one hour. Patients will be instructed on the how to properly perform the irrigation using a pre-recorded video demonstration. If no first-course DLT occurs then patients will continue taking the topical Verapamil dose BID. Patients will then return for follow-up visits at 1 week and 4 weeks. Subjective and objective outcome measures will be collected at each visit.

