4.2.1 PRIMARY ENDPOINT

Phase Ib:

The primary outcome measurement for Phase IB(SA1) will be defining the Maximal Tolerated Dose(MTD) of topical Verapamil HCl. Dose Limiting Toxicity will be defined as a development of 2nd or 3rd degree heart block as measured by an EKG.

Phase II:

The primary outcome for Phase II(SA2) will be determining the efficacy of topical Verapamil HCl at the MTD for subjective symptoms of CRSwNP using the validated SNOT-22.

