10 STATISTICAL CONSIDERATIONS

10.1 STATISTICAL AND ANALYTICAL PLANS

All statistical analyses will be performed in conjunction with the consultant biostatistician([name]). The proposed sample size of 20 subjects for the Phase II expansion cohort was determined to detect, with an 80% power at a 5% type-1 error rate, a change of 15.9 points on the primary endpoint (ie. SNOT-22 score) between baseline and 4 weeks. This calculation was based on two assumptions. The first is a target effect size of 15.9 which represents a conservative value derived from the established MCID for the SNOT-22 of 8.9[65] and the LSM change in SNOT-22 of 27.7 derived from our previous trial of oral Verapamil(Section R.4.d)[19]. The second is an anticipated standard deviation of 24 which is calculated from the standard deviations of 30 both at the baseline and 8 week time point observed in our oral Verapamil trial and an r2 of 50% between the two time points. With a significance level of 0.05, a standard deviation of 24, and 80% power, a sample size of 20 would be needed to detect a difference of 15.9. Analysis of efficacy will be based on an intention-to-treat population that will include all enrolled patients. A mixed-effect model with repeated measures approach will be used to independently analyze the change in the SNOT-22, VAS, and LKS. An intraclass correlation coefficient (ICC) will be calculated to assess inter-rater agreement with respect to the LKS scores. Descriptive statistics will be used for demographics, baseline characteristics, and safety variables. Linear regression models will be fitted to examine the interaction effect between baseline characteristics, whole mucus and exosomal P-gp concentrations, mucus and irrigant cytokine concentrations, and treatment on change in SNOT-22 while adjusting for the baseline SNOT-22 score. Statistical analyses will be performed using the statistical software SAS (SAS Institute Inc., Cary, NC)

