10.6 MEASURES TO MINIMIZE BIAS

10.6.1 ENROLLMENT/ RANDOMIZATION/ MASKING PROCEDURES

Participants will be enrolled in the MEEI Sinus Center. Eligible patients will be informed about the trial by their physician in the Sinus Center. If they express interest a member of the study staff will enroll them after passing through all inclusion and exclusion criteria. There will be no blinding or randomization in either phase of this trial.

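### Phase II reads a within-arm SNOT-22 change as verapamil efficacy, but the drug is given in a twice-daily 240 mL saline rinse that participants are not shown to be using already, so drug and vehicle effects cannot be separated

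*Combined protocol and SAP*

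**What the plan says.** - **Null hypothesis (10.2).** For SNOT-22: "There is no means difference between baseline SNOT-22 scores and 4 week SNOT-22 scores". Section 10.4.2 tests baseline against later visits by a t-test or a rank test, and section 10.1 also names a repeated-measures mixed model. Every comparison is within the one arm.
- **What the result is said to show (4.2.1).** The Phase II primary outcome is "determining the efficacy of topical Verapamil HCl at the MTD for subjective symptoms" of CRSwNP.
- **Control (10.6.1).** "There will be no blinding or randomization in either phase of this trial".
- **Intervention (4.1, Arm 2).** Twenty patients are "administered the MTD of topical Verapamil HCl in a 240mL buffered normal nasal rinse for 4 weeks BID". Sections 6.1.2 and 6.1.4 identify the vehicle as a commercial sinus rinse that the patient makes up at each use and to which the verapamil is added.
- **Rinse use before baseline.** The Phase 2 inclusion list (5.1), the exclusions (5.2) and the concomitant-treatment rules (7.5.1, 7.6) do not mention saline irrigation. The only washout (7.3.1) is three weeks for systemic steroids. An intake questionnaire is given at screening, but its items are not shown.
- **Sample size (10.1, 10.5).** N = 20 is set to detect "a change of 15.9 points on the primary endpoint (ie. SNOT-22 score) between baseline and 4 weeks", "with an 80% power at a 5% type-1 error rate".

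**The concern.** The treatment has two parts: verapamil, and a high-volume buffered saline irrigation used twice a day for four weeks. For a patient who was not irrigating before, both begin with the first dose. The baseline score then reflects neither part and the week 4 score reflects both. No analysis within one arm can divide the change between them. The regression in section 10.1 that refers to an interaction with treatment does not help, because everyone is treated.

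The 5% error rate protects the statement that nothing changed. It does not protect the statement that verapamil does nothing beyond its vehicle, which is the one a reader of section 4.2.1 will want. If the rinse alone relieves symptoms, the trial can be positive with an inert drug. Section 2.3.2 expects success to establish the drug as a treatment option and to clarify mechanism, so the attribution matters for what follows this trial.

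**Working it through.** **Inputs**
- n = 20, single arm; alpha 0.05; power 80%; target change 15.9 points; SD of change 24; MCID 8.9 points (all from 10.1, most repeated in 10.5).
- Sidedness is not stated. Two-sided is used because it reproduces N.
- The effect of the saline rinse is not in the documents, so a range is assumed.
- The share of participants new to rinsing is not in the documents. All and half are shown.

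**Step 1. Reproduce the plan's figure.** For a one-sample t-test on change, the noncentrality is δ√n/SD = 15.9 × √20 / 24 = 2.963 with 19 degrees of freedom. The two-sided critical value is 2.093, and power is 80.2%. At n = 19 it is 78.0%. So N = 20 reproduces as a two-sided test of mean change against zero.

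**Step 2. What rejects the null.** With the observed SD at 24, the standard error is 24/√20 = 5.367. The null is rejected when the observed mean change exceeds 2.093 × 5.367 = 11.2 points in size, whatever caused it.

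**Step 3. Inert verapamil, rinse effect in everyone.** Put an assumed cohort-wide rinse shift v in place of δ, so that the noncentrality is v√20/24.

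| Assumed shift v | Noncentrality | Chance of p<0.05 |
|---|---|---|
| 0 | 0 | 5% |
| 5 | 0.932 | 14% |
| 8.9 (the plan's MCID) | 1.658 | 35% |
| 15.9 (the plan's target) | 2.963 | 80% |

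The last row equals the design power by construction, because it gives the rinse the whole target effect.

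**Step 4. Only half the cohort new to rinsing.** The mean shift is halved, and the SD is kept at 24 for simplicity.
- 8.9 points in new rinsers: mean 0.5 × 8.9 = 4.45, noncentrality 0.829, chance 12%.
- 15.9 points in new rinsers: mean 0.5 × 15.9 = 7.95, noncentrality 1.481, chance 29%.

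**Step 5. Sensitivity to the SD.** Section 10.1 derives the 24 from SDs of 30 at both times and an r² of 50%. With r = √0.5 = 0.707, that gives 30 × √(2 × (1 − 0.707)) = 22.96, slightly below 24.
- At SD 22.96, cohort-wide shifts of 8.9 and 15.9 give 38% and 84%.
- At SD 30, they give 24% and 61%.

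**The case against.** The strongest reply is that this is a declared design choice. The plan says openly that Phase II is an uncontrolled, open-label expansion cohort. It follows the group's placebo-controlled oral trial (2.1), and no passage sets a go/no-go rule or says that rejecting the null proves causation. A pre-post null of zero is usual in such a cohort. That stands as a defence of the single arm. It does not defend labelling the result as efficacy of the drug when the vehicle is itself a new regimen for some participants.

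Three stronger readings are tempting, and the documents do not support them.

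- **That any change from zero would count.** It would not. About 11.2 points must be observed at SD 24, which is more than the 8.9-point MCID, so a small vehicle effect would usually miss significance.
- **That the Intake Form omits prior rinse use.** The form is not shown. Section 7.3.1 says only that it covers disease-relevant medical parameters, and rinse use could be one of them. What can be said is that no entry criterion or run-in deals with it.
- **That the false-positive risk is 35% or 80%.** Those figures assume an effect size the documents do not give, in every participant. Phase 2 patients are post-operative (5.1), with no surgery in the three months before enrolment (5.2). Some may already rinse, and how many is not stated. Step 4 of the working shows how far the figures fall when half do.

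**Conclusion.** The concern holds in this form: a significant SNOT-22 change in Phase II cannot be attributed to verapamil, because for participants new to irrigation the drug and its saline vehicle start at the same moment and nothing in the documents prevents or measures this.

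The size depends on two unknowns, the effect of the rinse and the share of participants new to it. Across the assumed values, with inert verapamil, n = 20, SD 24 and a two-sided 5% test, the chance of a significant result runs from 12% (8.9 points in half the cohort) to 80% (15.9 points in all), against a nominal 5%. These figures illustrate the exposure and do not predict it.

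Two further sources of non-drug change are present whatever the rinse history: regression to the mean from the SNOT-22 entry threshold of 30 (5.1), and self-report by participants who know what they are taking. The design is acceptable for an early-phase cohort. The entry conditions and the claim need to change.

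**What to change.** Keep the single arm and N = 20, and make two changes.

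1. **Section 5.1, Phase 2 inclusion.** Add stable use of a plain saline rinse, of similar volume and frequency to the study rinse, before the baseline SNOT-22. The sponsor should define the period. The vehicle is then in use at both baseline and week 4. The cost is a short delay for patients not yet rinsing, or slightly narrower eligibility; some may no longer score 30 or more at baseline. If this is not adopted, record prior rinse type, volume and frequency at intake (if the form does not already do so) and report the SNOT-22 change descriptively by prior use. With 20 patients that split will be imprecise.

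2. **Sections 4.2.1 and 10.2.** Describe the result as change during verapamil-in-saline irrigation, give its 95% CI, and set it against the 8.9-point MCID. Reserve efficacy of verapamil for a controlled comparison. This is needed even with change 1, which does not remove regression to the mean or open-label reporting. It costs only a narrower claim. The CI should be descriptive: its half-width is about 11.2 points at SD 24, so its limit nearer zero would clear 8.9 only if the observed improvement exceeded 8.9 + 11.2 = 20.1 points.

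A randomised saline control is not asked for here. At the same 15.9-point difference, SD 24, two-sided 5% and 80% power, it would need 2 × (24 × (1.960 + 0.842)/15.9)² ≈ 36 per arm (37 by the t distribution), or 72 to 74 patients in all.

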10.3 ANALYSIS DATASETS

Phase Ib:

All patients in the Phase Ib arm will be part of the Safety Analysis Dataset

Phase II:

The Phase II participants will be included in an intention-to-treat dataset and a safety analysis dataset.

Participants who used at least 80% of the topical verapamil during the one month period will be considered an evaluable dataset.

10.4 DESCRIPTION OF STATISTICAL METHODS

10.4.1 GENERAL APPROACH

Phase Ib:

Phase Ib will be an intra-pateint, accelerated titration design. The analysis of the safety endpoints will be presented with means and standard deviations of their occurance within the study population.

Phase II:

Phase II will be an open-label trial. Efficacy and safety outcomes will be presented with means and standard deviations.

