4.2.2 SECONDARY ENDPOINTS

Phase Ib:

Intermediate toxicity will be defined as: a heart rate of <50, an asymptomatic BP reduction >30% from baseline or SBP <90mmHg, an asymptomatic AMP reduction >30% from baseline or MAP<55, an asymptomatic DBP reduction >30% from baseline, and a Meltzer Compliance Grade >4.

Mild toxicity will be defined as a Meltzer Compliance Grade of 2-3.

Phase II:

The secondary outcomes of Phase II will be to determine the efficacy of Verapamil HCl at the MTD as measured by a subjective 10cm visual analog scale(VAS), Meltzer topical irrigation satisfaction and compliance scores, and the validated Lund-Kennedy nasal endoscopy score(LKS).

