6.1.7 STARTING DOSE AND DOSE ESCALATION SCHEDULE

Phase Ib Verapamil HCl dose will start at a total residual dose of 0.3mg. Dose escalations will be as follows: 0.3mg, 0.6mg, 1.2mg, 2.4mg, 3.0mg, 3.6mg. Participants will remain on a dose for at least one week before escalating.

Phase II dose will be determined by Phase Ib.

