8 ASSESSMENT OF SAFETY

8.1 SPECIFICATION OF SAFETY PARAMETERS

Safety parameters that are also endpoints for Phase Ib are:

- a development of 2nd or 3rd degree heart block as measured by an EKG.
- a heart rate of <50
- an asymptomatic BP reduction >30% from baseline or SBP <90mmHg
- an asymptomatic AMP reduction >30% from baseline or MAP<55
- an asymptomatic DBP reduction >30% from baseline

All safety parameters will be recorded in a partcipants CRF at each study visit. All AEs will require reporting for the protection of human subjects.

If a heart block develops, treatment will be adjusted based on symptomatology. Completely asymptomatic patients can be observed. Patients with mild to moderate symptoms (hypotension, orthostasis, fatigue, dyspnea or angina) should be treated with 1liter NS bolus followed by Calcium Gluconate. Patients who are severely symptomatic and have failed the above interventions can also receive glucagon, norepinephrine, and finally pacing if necessary

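### Safety events are to be reported as means and SDs, with no by-dose table for Phase Ib and no interval for any event proportion

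*Combined protocol and SAP*

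**What the plan says.** For Phase Ib, section 10.4.1 gives the safety endpoints as "means and standard deviations of their occurance within the study population". For Phase II it states: "Efficacy and safety outcomes will be presented with means and standard deviations".

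The endpoints concerned are largely events. Section 4.2.1 says "Dose Limiting Toxicity will be defined as a development of 2nd or 3rd degree heart block as measured by an EKG", and section 8.1 lists the same event among the safety parameters. Section 4.2.2 builds intermediate toxicity (IT) from cut-offs: "Intermediate toxicity will be defined as: a heart rate of <50, an asymptomatic BP reduction >30% from baseline or SBP <90mmHg", with further limits on mean arterial pressure, diastolic pressure and the Meltzer compliance grade.

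Phase Ib takes a participant through up to six dose levels. Section 6.1.7 says "Dose escalations will be as follows: 0.3mg, 0.6mg, 1.2mg, 2.4mg, 3.0mg, 3.6mg". The only Phase Ib analysis set in section 10.3 covers everyone: "All patients in the Phase Ib arm will be part of the Safety Analysis Dataset".

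Other text on summarising safety:
- Section 10.1 promises descriptive statistics for safety variables and goes no further.
- Section 10.4.4 plans an adverse-event rate for each phase and treats 10% as significant. It does not mention dose, what is counted, or an interval.
- Section 10.4.6 provides for counts with percentages, but only at baseline.
- Section 10.4.10 lists individual Phase Ib data by visit number rather than by dose.

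**The concern.** A mean and SD describe the spread of a measurement. Applied to whether an event occurred, the mean is the event proportion and the SD is a fixed function of it, so the second number adds nothing and is not a measure of precision. The problem is sharpest when no events are seen. That is a plausible result for heart block, and it would print as zero with zero spread whether three participants or 20 had been treated.

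Phase Ib raises a further question of layout. Its purpose is to relate toxicity to dose, and one participant contributes to several doses. A single figure for the study population, with no dose-level table planned, need not show where the events fell. It also leaves open whether the denominator is participants or participant-courses.

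Safety at the selected dose is part of a primary Phase II objective (section 3), so a reader needs to know what rates about 20 participants can and cannot exclude.

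**Working it through.** **The plan's own figure.** The plan gives no figure for the precision of a safety rate. The relevant computed number is the Phase II size of 20 (sections 10.1 and 10.5), which sets the safety denominator. It reproduces: standardised effect 15.9/24 = 0.6625, paired t-test, 80% power, two-sided 5% level (sidedness is my assumption, as the plan does not state it) gives n = 19.9, so 20. Power at 20 is 80.2%.

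**What the planned summary would print, and what the data would support.** For x participants with an event out of n, let p = x/n.
- Mean = p.
- Sample SD = √[p(1 − p) × n/(n − 1)]. For 1/20: √(0.05 × 0.95 × 20/19) = √0.05 = 0.22.
- Clopper-Pearson 95% limits: lower = 2.5% point of Beta(x, n − x + 1); upper = 97.5% point of Beta(x + 1, n − x). For x = 0 the lower limit is 0 and the upper is 1 − 0.025^(1/n). For n = 20 that is 1 − 0.832 = 16.8%.

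The plan gives no expected event rates, so these counts are illustrative:

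| Events / participants | Mean (SD) | Exact 95% CI |
|---|---|---|
| 0/20 | 0 (0) | 0 to 16.8% |
| 1/20 | 0.05 (0.22) | 0.1 to 24.9% |
| 2/20 | 0.10 (0.31) | 1.2 to 31.7% |
| 0/6 | 0 (0) | 0 to 45.9% |
| 0/3 | 0 (0) | 0 to 70.8% |

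The three zero-event rows print identically, while their upper limits run from 16.8% to 70.8%.

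**The 10% threshold in section 10.4.4.** With 20 participants, 10% is two participants. P(at least 2 of 20) = 1 − (1 − π)^20 − 20π(1 − π)^19. If the true rate π is 5%, this is 26%; if π is 10%, it is 61%. An observed rate on either side of 10% is therefore weak evidence by itself, and even 0/20 does not exclude a true rate of 10%.

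**Dose in Phase Ib.** Assume three participants at each of six doses (18 participant-courses), two dose-limiting toxicities (DLTs) at one dose and none elsewhere. If courses are combined, the summary is 2/18, or 0.11 (SD 0.32). At the dose concerned the result is 2/3, which meets the section 4.1 definition of the maximal administered dose.

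**Counting ITs.** Section 6.1.8 withholds escalation after a DLT or two ITs on the previous dose, and section 5.4.1 removes a participant with more than one IT. A participant can therefore have more than one IT. Section 4.1 sets the maximal administered dose at two or more DLTs, or four or more ITs. In a cohort of three, four ITs require at least one participant with a repeat. A count of participants with an IT would lose that information, so both counts are needed.

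**The case against.** The strongest reply is that little depends on this sentence. Section 4.1 assigns the maximal administered and tolerated doses from event counts at a dose, and section 10.4.7.1 has the safety endpoints monitored at every weekly Phase Ib visit. Section 10.4.4, the dedicated safety section, plans an event rate. The mean of a 0/1 variable is the proportion, so the point estimate survives. The Phase II sentence also covers continuous heart rate and blood pressure, for which a mean and SD are suitable. Individual listings would allow re-tabulation by dose if dose is attached to each visit.

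All of this stands, and it limits the point. It does not supply a by-dose Phase Ib table, a counting unit for the section 10.4.4 rate, or an interval for any proportion.

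A reader might infer more than the documents support:
- That dose-finding rests on a pooled mean. Section 4.1 uses counts at a dose.
- That the plan orders doses to be pooled. Section 10.4.1 is silent on dose; pooling is an inference from its reference to the study population and the lack of a dose-level table.
- That dose is obscured in Phase II. That phase uses one unchanged dose (section 6.1.8).
- That mean ± SD would serve as a confidence interval and so include negative rates. The plan never offers it as one.
- That every toxicity is strictly yes/no. ITs can recur within a participant, so a mean number per participant has some meaning for them.

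One objection bears on the remedy. Phase Ib cohort size depends on the events seen, so a fixed-n interval is not strictly exact there, and in cohorts of one to three participants it says little.

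**Conclusion.** The point holds as a defect in safety reporting and estimation. For event endpoints the planned SD is redundant and carries no information about precision. In Phase II, 0 (SD 0) could stand for a true rate as high as 16.8%, and 0.05 (SD 0.22) for anything from 0.1% to 24.9%. In Phase Ib, no section commits to showing toxicity by dose.

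The escalation rule, sample size and efficacy analysis are unaffected. The figures assume 20 participants dosed in Phase II. Because section 5.4.1 replaces withdrawals, the number dosed may be larger and the intervals somewhat narrower. The event counts and the 18-course example are illustrations, not predictions.

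**What to change.** In section 10.4.1, replace mean and SD for event endpoints with:

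- **Phase Ib, by dose level:** participants with a DLT, and participants with at least one IT, each over participants exposed at that dose; plus the total number of ITs at that dose. Label any intervals as descriptive, because cohort size depends on the observed events.
- **Phase II:** participants with each event over all participants dosed, including those later withdrawn and replaced, with Clopper-Pearson 95% confidence intervals.

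In section 10.4.4, state the counting unit for the adverse-event rate, report it in the same form, and give the Phase II rate with the same interval. Keep mean (SD) for continuous changes in heart rate, blood pressure and mean arterial pressure, by dose in Phase Ib.

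The cost is SAP wording and table shells. Sample size, visits, data collection and clinical management do not change.
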